### **CONTRACEPTION GUIDANCE FOR MALE PARTICIPANTS WITH PARTNER(S) OF CHILDBEARING POTENTIAL.**

Male participants with female partners of childbearing potential are eligible to participate if they agree to the following during the treatment and until the end of relevant systemic exposure.

- Inform any and all partner(s) of their participation in a clinical drug study and the need to comply with contraception instructions as directed by the investigator.
- Male participants are required to use a condom for study duration and until the end of relevant systemic exposure defined as 90 days after the end of treatment in the male participant.
- Female partners of males participating in the study to consider use of effective methods of contraception until the end of relevant systemic exposure, defined as 90 days after the end of treatment in the male participant.
- Male participants with a pregnant or breastfeeding partner must agree to remain abstinent from penile vaginal intercourse or use a male condom during each episode of penile penetration during the treatment and until 90 days after the end of treatment.
- Refrain from donating sperm for the duration of the study treatment and for 90 days after the end of treatment.

## **COLLECTION OF PREGNANCY INFORMATION**

Guidance for collection of Pregnancy Information and outcome of pregnancy on the Pregnancy Surveillance Form is provided in [Section 8.5.6](#) and [APPENDIX 3](#).

## APPENDIX 5 SYSTEMIC LUPUS INTERNATIONAL COLLABORATING CLINICS CLASSIFICATION CRITERIA FOR SYSTEMIC LUPUS ERYTHEMATOSUS

Requirements: ≥ 4 criteria (at least 1 clinical and 1 laboratory criteria)  
OR biopsy-proven lupus nephritis with positive ANA or Anti-DNA

### Clinical Criteria

1. Acute Cutaneous Lupus\*
2. Chronic Cutaneous Lupus\*
3. Oral or nasal ulcers \*
4. Non-scarring alopecia
5. Arthritis \*
6. Serositis \*
7. Renal \*
8. Neurologic \*
9. Hemolytic anemia
10. Leukopenia \*
11. Thrombocytopenia (<100,000/mm^3)

### Immunologic Criteria

1. ANA
2. Anti-DNA
3. Anti-Sm
4. Antiphospholipid Ab \*
5. Low complement (C3, C4, CH50)
6. Direct Coombs' test (do not count in the presence of hemolytic anemia)

#### Notes:

#### CLINICAL CRITERIA

##### (1) Acute Cutaneous Lupus OR Subacute Cutaneous Lupus

- Acute cutaneous lupus: lupus malar rash (do not count if malar discoid), bullous lupus, toxic epidermal necrolysis variant of SLE, maculopapular lupus rash, photosensitive lupus rash (in the absence of dermatomyositis)
- Subacute cutaneous lupus: nonindurated psoriaform and/or annular polycyclic lesions that resolve without scarring, although occasionally with postinflammatory dyspigmentation or telangiectasias)

##### (2) Chronic Cutaneous Lupus

Classic discoid rash localized (above the neck) or generalized (above and below the neck), hypertrophic (verrucous) lupus, lupus panniculitis (profundus), mucosal lupus, lupus erythematosus tumidus, chilblains lupus, discoid lupus/lichen planus overlap

##### (3) Oral Ulcers OR Nasal Ulcers

- Oral: palate, buccal, tongue
- Nasal ulcers
- In the absence of other causes, such as vasculitis, Behçet's disease, infection (herpes virus), inflammatory bowel disease, reactive arthritis, and acidic foods

**(4) Nonscarring alopecia**

Diffuse thinning or hair fragility with visible broken hairs, in the absence of other causes such as alopecia areata, drugs, iron deficiency, and androgenic alopecia

**(5) Synovitis involving 2 or more joints**

- Characterized by swelling or effusion
- OR tenderness in 2 or more joints and at least 30 minutes of morning stiffness

**(6) Serositis**

- Typical pleurisy for more than 1 day OR pleural effusions OR pleural rub
- Typical pericardial pain (pain with recumbency improved by sitting forward) for more than 1 day OR pericardial effusion OR pericardial rub OR pericarditis by electrocardiography
- In the absence of other causes, such as infection, uremia, and Dressler's pericarditis

**(7) Renal**

Urine protein-to-creatinine ratio (or 24-hour urine protein) representing 500 mg protein per 24 hours OR red blood cell casts

**(8) Neurologic**

Seizures, psychosis, mononeuritis multiplex (in the absence of other known causes such as primary vasculitis), myelitis, peripheral or cranial neuropathy (in the absence of other known causes such as primary vasculitis, infection, and diabetes mellitus), acute confusional state (in the absence of other causes, including toxic/metabolic, uremia, drugs)

**(9) Hemolytic anemia**

**(10) Leukopenia (< 4000/mm^3) OR Lymphopenia (< 1000/mm^3)**

- Leukopenia at least once: In the absence of other known causes such as Felty's syndrome, drugs, and portal hypertension.
- Lymphopenia at least once: in the absence of other known causes such as corticosteroids, drugs, and infection

**(11) Thrombocytopenia (< 100,000/mm^3)**

At least once in the absence of other known causes such as drugs, portal hypertension, and thrombotic thrombocytopenic purpura

**IMMUNOLOGIC CRITERIA**

**(1) ANA level above laboratory reference range**

**(2) Anti-dsDNA antibody level above laboratory reference range (or 2-fold the reference range if tested by enzyme-linked immunosorbent assay); indeterminate results are considered positive**

**(3) Anti-Sm: presence of antibody to Sm nuclear antigen**

- (4) Antiphospholipid antibody** positivity, as determined by
- Positive test for lupus anticoagulant
  - False-positive test result for rapid plasma reagin
  - Medium- or high-titer anticardiolipin antibody level (IgA, IgG, or IgM)
  - Positive test result for anti- $\beta$ -glycoprotein I (IgA, IgG, or IgM)
- (5) Low complement** (C3, C4, or CH50)
- (6) Direct Coombs test** (in the absence of hemolytic anemia)

Reference:

**APPENDIX 6 COMMONLY USED CORTICOSTEROID EQUIVALENTS**

Medication	Dose Equivalence
Prednisone	20 mg
Cortisone	100 mg
Hydrocortisone	80 mg
Deflazacort	26 mg
Prednisolone	20 mg
Methylprednisolone	16 mg
Triamcinolone	16 mg
Budesonide	4 mg
Dexamethasone	3 mg
Betamethasone	2.4 mg

**APPENDIX 7                      REQUIRED RECOVERY (WASHOUT) TIMES FOR SPECIFIC  
MEDICATIONS PRIOR TO SCREENING**

Medications	Discontinuation Prior to Signing Consent
Abatacept (CTLA4Ig)	12 weeks
Acthar ® gel (repository corticotropin injection)	6 weeks
Adalimumab	12 weeks
Alefacept	8 weeks
AMG 623	12 weeks
Anakinra	12 weeks
Apremilast	4 weeks
Atacicept (TACI-Ig)	48 weeks
Azathioprine	4 weeks
Belimumab	12 weeks
BIIB059	15 weeks
Certolizumab pegol	24 weeks
Cyclophosphamide	24 weeks
Cyclosporine	4 weeks for systemic use (oral, IV, etc)
Eculizumab	12 weeks
Efalizumab	8 weeks
Etanercept	4 weeks
Infliximab	12 weeks
Intravenous immunoglobulin	24 weeks
Leflunomide	36 weeks
Lenalidomide with cholestyramine	24 weeks
Lulizumab	6 weeks
Lupuzor (IPP-201101)	12 weeks
Methotrexate	4 weeks
Natalizumab	12 weeks
Obinutuzumab	26 weeks
Ocrelizumab	24 weeks
Ofatumumab	26 weeks
Plasmapheresis	24 weeks
Retinoids (oral isotretinoin and acitretin; topical retinoids are allowed)	4 weeks

Medications	Discontinuation Prior to Signing Consent
Rituximab	52 weeks
Sirolimus	4 weeks
Sulfasalazine	4 weeks
Tabalumab	14 weeks
Tacrolimus	4 weeks for systemic use (oral, IV, etc)
Thalidomide	4 weeks
Tocilizumab	12 weeks
Voclosporin	4 weeks

## APPENDIX 8      **DIAGNOSTIC CRITERIA FOR SUBSTANCE DEPENDENCE AND ABUSE**

The following is from the Diagnostic and Statistical Manual of Mental Disorders, 4th edition:

### Diagnostic Criteria for Psychoactive Substance Dependence

A maladaptive pattern of substance use, leading to clinically significant impairment or distress as manifested by 3 (or more) of the following, occurring at any time in the same 12-month period:

- 1) Tolerance, as defined by either of the following:
  - a) A need for markedly increased amounts of the substance to achieve intoxication or desired effect
  - b) Markedly diminished effect with continued use of the same amount of the substance
- 2) Withdrawal, as manifested by either of the following:
  - a) The characteristic withdrawal syndrome for the substance
  - b) The same (or closely related) substance is taken to relieve or avoid withdrawal symptoms
- 3) The substance is often taken in larger amounts or over a longer period than was intended
- 4) There is a persistent desire or unsuccessful efforts to cut down or control substance use
- 5) A great deal of time is spent in activities necessary to obtain the substance (eg, visiting multiple doctors or driving long distances), use the substance (eg, chain-smoking), or recover from its effects
- 6) Important social, occupational, or recreational activities are given up or reduced because of substance use
- 7) The substance use is continued despite knowledge of having a persistent or recurring physical or psychological problem that is likely to have been caused or exacerbated by the substance (eg, current cocaine use despite recognition of cocaine-induced depression, or continued drinking despite recognition that an ulcer was made worse by alcohol consumption.)

### Criteria for Severity of Psychoactive Substance Dependence

**Mild:** Few, if any, symptoms in excess of those required to make the diagnosis, and the symptoms result in no more than mild impairment in occupational functioning or in usual social activities or relationships with others.

**Moderate:** Symptoms or functional impairment between “mild” and “severe.”

[figure not shown]
**Severe:** Many symptoms in excess of those required to make the diagnosis, and the symptoms markedly interfere with occupational functioning or with usual social activities or relationships with others.

[figure not shown]
**In Partial Remission:** During the past 6 months, some use of the substance and some symptoms of dependence.

**In Full Remission:** During the past 6 months, either no use of the substance, or use of the substance and no symptoms of dependence.

Diagnostic Criteria for Psychoactive Substance Abuse

- A. A maladaptive pattern of psychoactive substance use, leading to clinically significant impairment or distress as manifested by 1 (or more) of the following, occurring at any time in the same 12-month period:
- 1) Recurrent substance use resulting in a failure to fulfill major role obligations at work, school, or home (eg, repeated absences or poor work performance related to substance use; substance-related absences, suspensions, or expulsions from school, neglect of children or household)
  - 2) Recurrent substance use in situations in which it is physically hazardous (eg, driving an automobile or operating a machine when impaired by substance use)
  - 3) Recurrent substance-related legal problems (eg, arrests for substance-related disorderly conduct)
  - 4) Continued substance use despite having persistent or recurrent social or interpersonal problems caused or exacerbated by the effects of the substance (eg, arguments with spouse about consequences of intoxication, physical fights)
- B. The symptoms have never met the criteria for substance dependence for this class of substance

APPENDIX 10

[figure not shown]
SYSTEMIC LUPUS INTERNATIONAL COLLABORATING CLINICS/AMERICAN COLLEGE OF RHEUMATOLOGY DAMAGE INDEX

[figure not shown]
SYSTEMIC LUPUS INTERNATIONAL COLLABORATING CLINICS	
Patient Name: _____ Study No. _____	
Assessment Date: ____/____/____	
Damage occurring since diagnosis of lupus, ascertained by clinical assessment and present for at least 6 months unless otherwise stated. Repeat episodes mean at least 6 months apart to score 2. The same lesion cannot be scored twice.	
ITEM	SCORE (circle)
OCULAR (Either eye, by clinical assessment)	
Any cataract ever	0 1
Retinal change OR Optic atrophy	0 1
NEUROPSYCHIATRIC	
Cognitive impairment (e.g. memory deficit, difficulty with calculation, poor concentration, difficulty in spoken or written language, impaired performance level)	
OR Major psychosis	0 1
Seizures requiring therapy for 6 months	0 1
Cerebral vascular accident ever (Score 2 if >1), resection not for malignancy	0 1 2
Cranial or peripheral neuropathy (excluding optic)	0 1
Transverse myelitis	0 1
RENAL	
Estimated or measured GFR <50%	0 1
Proteinuria 24 h, ≥ 3.5 g	0 1
OR	
End-stage renal disease (regardless of dialysis or transplantation)	3
PULMONARY	
Pulmonary hypertension (right ventricular prominence, or loud P2)	0 1
Pulmonary fibrosis (physical and X-ray)	0 1
Shrinking lung (X-ray)	0 1
Pleural fibrosis (X-ray)	0 1
Pulmonary infarction (X-ray) OR resection not for malignancy	0 1
CARDIOVASCULAR	
Angina OR coronary artery bypass	0 1
Myocardial infarction ever (Score 2 if >1)	0 1 2
Cardiomyopathy (ventricular dysfunction)	0 1
Valvular disease (diastolic murmur, or a systolic murmur > 3/6)	0 1
Pericarditis x 6 months or pericardectomy	0 1
PERIPHERAL VASCULAR	
Claudication x 6 months	0 1
Minor tissue loss (pulp space)	0 1
Significant tissue loss ever (eg. loss of digit or limb, resection) (Score 2 if >1)	0 1 2
Venous thrombosis with swelling, ulceration, OR venous stasis	0 1
GASTROINTESTINAL	
Infection or resection of bowel (below duodenum), spleen, liver or gall bladder ever (Score 2 if >1)	0 1 2
Mesenteric insufficiency	0 1
Chronic peritonitis	0 1
Stricture OR upper gastrointestinal tract surgery ever	0 1
Pancreatic insufficiency requiring enzyme replacement or with pseudocyst	0 1
MUSCULOSKELETAL	
Atrophy or weakness	0 1
Deforming or erosive arthritis (including reducible deformities, excluding avascular necrosis)	0 1
Osteoporosis with fracture or vertebral collapse (excluding avascular necrosis)	0 1
Avascular necrosis (Score 2 if >1)	0 1 2
Osteomyelitis	0 1
Ruptured tendons	0 1
SKIN	
Alopecia	0 1
Extensive scarring or panniculom other than scalp and pulp space	0 1
Skin ulceration (excluding thrombosis) for more than 6 months	0 1
PREMATURE GONADAL FAILURE	0 1
DIABETES (regardless of treatment)	0 1
MALIGNANCY (Exclude dysplasia)	0 1 2

[figure not shown]
Reference:

[figure not shown]

[figure not shown]

[figure not shown]

**APPENDIX 12 INTERNATIONAL SOCIETY OF NEPHROLOGY/RENAL PATHOLOGY SOCIETY 2003 CLASSIFICATION OF LUPUS NEPHRITIS**

ISN/RPS Class	Description of Lupus Nephritis Features
I	Minimal mesangial
II	Mesangial proliferative
III	Focal
	III (A): active lesions: focal proliferative
	III (A/C): active and chronic lesions: focal proliferative and sclerosing
	III (C): chronic inactive lesions with glomerular scars: focal sclerosing
IV	Diffuse
	IV-S: diffuse segmental
	IV-S (A): active lesions: diffuse segmental proliferative
	IV-S (A/C): active and chronic lesions: diffuse segmental proliferative and sclerosing
	IV-S (C): chronic inactive lesions with scars: diffuse segmental sclerosing
	IV-G: diffuse global
	IV-G (A): active lesions: diffuse global proliferative
	IV-G (A/C): active and chronic lesions: diffuse global proliferative and sclerosing
	IV-G (C): chronic inactive lesions with scars: diffuse global sclerosing
V	Membranous
VI	Advanced sclerotic

Reference:

## APPENDIX 13      **UPDATED CLASSIFICATION CRITERIA FOR ANTIPHOSPHOLIPID SYNDROME**

Antiphospholipid antibody syndrome (APS) is present if at least one of the following clinical criteria and one of the laboratory criteria are met†:

### **Clinical Criteria**

1. Vascular thrombosis: one or more clinical episodes‡ of arterial, venous, or small vessel thrombosis§ in any tissue or organ; thrombosis must be confirmed by objective validated criteria, ie, unequivocal findings of appropriate imaging studies or histopathology (for histopathologic confirmation, thrombosis should be present without significant evidence of inflammation in the vessel wall)
2. Pregnancy morbidity, defined as one of the following:
  - a) One or more unexplained deaths of a morphologically normal fetus at or beyond the 10th week of gestation, with normal fetal morphology documented by ultrasound or by direct examination of the fetus
  - b) One or more premature births of morphologically normal neonate before the 34th week of gestation because of one of the following:
    - i. Eclampsia or severe pre-eclampsia defined according to the standard definitions
    - ii. Recognized features of placental insufficiency\*\*
  - c) Three or more unexplained consecutive spontaneous abortions before the 10th week of gestation, with maternal anatomic or hormonal abnormalities and paternal and maternal chromosomal causes excluded

### **Laboratory Criteria**

1. Lupus anticoagulant present in plasma on two or more occasions at least 12 weeks apart, detected according to the guidelines of the International Society on Thrombosis and Haemostasis (Scientific Subcommittee on LAs/phospholipid-dependent antibodies)
2. Anticardiolipin antibody of IgG and/or IgM isotype in serum or plasma, present in medium or high titer (ie, > 40 IgG phospholipid units or IgM phospholipid units, or > 99th percentile) on two or more occasions at least 12 weeks apart, measured by standardized enzyme-linked immunosorbent assay (ELISA)

---

† Classification of APS should be avoided if fewer than 12 weeks or more than 5 years separate the positive antiphospholipid test and the clinical manifestation.

‡ A thrombotic episode in the past could be considered as a clinical criterion, provided that the thrombosis was proven by appropriate diagnostic means and that no alternative diagnosis or cause of thrombosis was found.

§ Superficial venous thrombosis is not included in the clinical criteria.

\*\* Generally accepted features of placental insufficiency include the following:

- Abnormal or nonreassuring fetal surveillance test(s), eg, a nonreactive nonstress test suggestive of fetal hypoxemia
- Abnormal Doppler flow velocimetry waveform analysis suggestive of fetal hypoxemia, eg, absent end-diastolic flow in the umbilical artery
- Oligohydramnios, eg, an amniotic fluid index of 5 cm or less
- A postnatal birth weight less than the 10th percentile for the gestational age

3. Anti- $\beta_2$  glycoprotein-I antibody of IgG and/or IgM isotype in serum or plasma (in titer > the 99th percentile), present on two or more occasions at least 12 months apart, measured by standardized ELISA, according to recommended procedures

Reference:

## **APPENDIX 14      DIAGNOSIS AND CLASSIFICATION OF CATASTROPHIC ANTIPHOSPHOLIPID SYNDROME**

A diagnosis of definite catastrophic antiphospholipid syndrome (CAPS) is made when all of the following 4 criteria are met:

1. Evidence of involvement of 3 or more organs, systems, and/or tissues
  - This usually means clinical evidence of vessel occlusions, confirmed by imaging techniques when appropriate
  - Renal involvement is defined by a 50% increase in serum creatinine, severe systemic hypertension (> 180/100 mmHg) and/or proteinuria (> 500 mg/24 hours)
2. Development of manifestations simultaneously or in less than 1 week
3. Confirmation by histopathology of small vessel occlusion in at least 2 organ or tissues
  - Significant evidence of thrombosis must be present, although vasculitis may coexist occasionally
4. Laboratory confirmation of the presence of antiphospholipid antibodies (APAs; lupus anticoagulant and/or anticardiolipin antibodies)
  - If the patient had not previously been diagnosed as having APS, the laboratory confirmation requires that the presence of APAs must be detected on 2 or more occasions at least 6 weeks apart (not necessarily at the time of the event), according to the proposed preliminary criteria for the classification of definite

Note: Probable CAPS may be diagnosed in the following situations:

- Criteria 1, 2, and 4 are met, but not 3
- Criteria 1, 3, and 4 are met; however, a third event occurs between a week and a month later, despite anticoagulation
- Criteria 1 through 4 are met, but only 2 organs/tissues are involved
- Criteria 1 through 4 are met, but APAs could not be assayed 6 weeks apart because the patient died and had never been tested before

## APPENDIX 15 MORPHINE MILLIGRAM EQUIVALENTS FOR OPIOIDS

The following table shows daily morphine milligram equivalents for some opioids. This list is not exhaustive, and the 30 mg morphine equivalence limit applies to all opioid analgesics even if they are not listed here.

Opioid	30 mg morphine equivalent
butorphanol	4.3 mg/day
codeine	200 mg/day
dihydrocodeine	120 mg/day
fentanyl transdermal	12.5 mcg/hr
hydrocodone	30 mg/day
hydromorphone	7.5 mg/day
levorphanol tartrate	2.7 mg/day
meperidine HCl	300 mg/day
oxycodone	20 mg/day
oxymorphone	10 mg/day
pentazocine	81.1 mg/day
tapentadol	75 mg/day
tramadol	300 mg/day

Reference:

Centers for Medicare and Medicaid Services. Opioid Oral Morphine Milligram Equivalent Conversion Factors. <https://www.cms.gov/Medicare/Prescription-Drug-Coverage/PrescriptionDrugCovContra/Downloads/Opioid-Morphine-EQ-Conversion-Factors-Aug-2017.pdf>. Accessed August 21, 2018.

**APPENDIX 16 OHIO SLE STUDY – CLASSIFICATION OF RENAL FLARE**

Flare Severity	Criteria
Mild	Increase in glomerular hematuria from < 5 to > 15 rbcs/hpf, with ≥ 2 acanthocytes/hpf and/or recurrence of ≥ 1 rbc cast, wbc cast (no infection), or both
Moderate	If baseline creatinine < 2 mg/dL, an increase of 0.2 to 1.0 mg/dL
	If baseline creatinine ≥ 2 mg/dL, an increase of 0.4 to 1.5 mg/dL, and/or if baseline UPCR < 0.5, an increase in UPCR to ≥1 mg/mg
	If baseline UPCR = 0.5 to 1 mg/mg, an increase in UPCR to ≥ 2 mg/mg
	If baseline UPCR >1 mg/mg, an increase of ≥ 2-fold with absolute UPCR < 5 mg/mg
Severe	If baseline creatinine < 2 mg/dL, an increase of > 1 mg/dL
	If baseline creatinine ≥ 2 mg/mg, an increase of > 1.5 mg/mg and/or an absolute increase in UPCR > 5 mg/mg

hpf = high-power field; rbc = red blood cell; UPCR = urine protein:creatinine ratio; wbc = white blood cell

Reference:

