**Table 2: Procedures and Assessments in Part A of Protocol IM011073 (Open-label MMF Run-in Period)**

Visit Number	A1	A2	A3	A4 a	Notes
Week/Day of MMF Treatment b	Day 1	Week 4±14d	Week 8±14d	Week 12±14d	Assessments at Visit A4 will be used to determine subjects' eligibility for randomization to IP/placebo or continuation with only open-label MMF/CS in Part B. These assessments will also be used to stratify subjects who are eligible for randomization.
AEs and SAEs	X	X	X	X	SAE collection begins at the time ICF is signed; AE collection begins at the time of the first MMF dose in Part A; see Section 8.5
Medical history	X				Any medical occurrences after signing the ICF but before the first dose of MMF in Part A will be recorded as medical history. Subjects already on MMF at screening should have medical history recorded at their first visit in Part A.
Body weight and vital signs	X	X	X	X	Blood pressure and heart rate should be measured after the subject has been resting quietly for at least 5 minutes.
Concomitant medications	X	X	X	X	
Complete physical examination	X	X	X	X	
Dispense MMF	X	X	X	X	
Baseline indices of disease activity and damage					
SDI				X	APPENDIX 10
Laboratory tests					
Routine chemistry and hematology	X	X	X	X	Results from Visit A4 will be the baseline values for Part B
CBC for MMF monitoring	As needed per MMF prescribing information				Weekly during the first month and every 2 weeks for the second and third month of MMF; may be performed at a local laboratory; sites will contact subjects in advance to remind them; see Section 6.2
ANA				X	

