### 3 OBJECTIVES AND ENDPOINTS

Objective	Endpoint
Primary – 52-week Blinded Treatment Period (Part B)	

 
Safety: To assess the safety and tolerability of BMS-986165 in subjects with LN
 
	
 
AEs, vital signs, ECGs, and laboratory abnormalities from baseline through Week 52
 

 
Efficacy: To evaluate the efficacy of BMS-986165 compared with placebo with regard to proteinuria
 
	
 
Percentage change from baseline in 24-hour UPCR at Week 24
 

Secondary– 52-week Blinded Treatment Period (Part B)	

 
Efficacy: To evaluate the efficacy of BMS-986165 with regard to measures of renal function and SLE activity
 
	
 
PRR at Week 24, defined as <math>\geq 50\%</math> reduction from baseline in 24-hour UPCR
 
CRR at Week 24, defined as both of the following:                             
 
24-hour UPCR <math>\leq 0.5</math> mg/mg
 
eGFR <math>\geq 60</math> mL/min or <math>\leq 20\%</math> decrease from baseline
 
 
 
CRR at Week 52
 
CRR + successful CS taper to <math>\leq 7.5</math> mg/day at Week 24
 
CRR + successful CS taper to <math>\leq 7.5</math> mg/day at Week 52
 
PRR at Week 52
 

AE = adverse event; C = complement; [redacted] CRR = complete renal response; CS = corticosteroid; [redacted] ECG = electrocardiogram; eGFR = estimated glomerular filtration rate; [redacted]  
[redacted] LN = lupus nephritis; NIH = National Institutes of Health; [redacted] OSS = Ohio SLE Study; [redacted]  
PRR = partial renal response; [redacted]  
[redacted] UPCR = urine protein:creatinine ratio

Note: 24-hour urine specimens will be used for the UPCR at baseline (Visit A4), Week 24 (Visit B7), and Week 52 (Visit B14).

Note: eGFR will be calculated using the Modification of Diet in Renal Disease (MDRD) equation

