## 4 STUDY DESIGN

### 4.1 Overall Design

This is a 3-part, multicenter, randomized, double-blind study to evaluate the efficacy and safety of BMS-986165 in combination with background treatment with MMF in subjects with LN International Society of Nephrology/Renal Pathology Society (ISN/RPS) Class III or IV (alone or in combination with Class V). Subjects will be assessed for renal response after having received a total of at least 12 weeks (but  $\leq 24$  weeks) of treatment with MMF at a target dose of 1.5 to 3.0 g/day (refer to [Section 6.1](#) for further details regarding individual target dose). Subjects will receive 12 weeks of target-dose MMF in Part A of the study if they have not been taking target-dose MMF at screening. Subjects who have been taking target-dose MMF for  $\geq 1$  day but  $< 12$  weeks at screening will continue to receive target-dose MMF in Part A until they reach 12 weeks of total MMF treatment. Subjects who have been taking target-dose MMF for  $\geq 12$  weeks but  $\leq 24$  weeks at screening will enter the study at Visit A4 to immediately be assessed for renal response and entry into Part B.

Subjects with an inadequate renal response to MMF may be randomized to blinded study treatment BMS-986165 3 mg BID, BMS-986165 6 mg BID, or placebo BID, as add-on therapy to MMF in Part B. Inadequate response is defined as  $< 50\%$  reduction in 24-hour urine protein:creatinine ratio (UPCR) from the pre-MMF value (refer to [Section 4.1.2.2](#)) and a 24-hour UPCR  $\geq 1.0$  mg/mg. Randomized subjects will continue taking open-label MMF with or without corticosteroids. Randomization will be stratified by baseline (Visit A4) 24-hour UPCR ( $< 3.0$  mg/mg versus  $\geq 3.0$  mg/mg) and total cumulative intravenous (IV) corticosteroid (IV methylprednisolone or

parenteral equivalent) dose given in the 16 weeks before randomization (< 250 mg versus  $\geq$  250 mg).

The total duration of participation in the study is up to [REDACTED] weeks, which includes the following periods:

- Screening period: approximately 28 days (this period may be extended up to 5 days if needed to complete screening procedures, with approval of the [REDACTED] medical monitor)
- Treatment period:
  - Part A: Open-label MMF (1.5 to 3.0 g/day) run-in period of up to 12 weeks, depending on duration of treatment with MMF at the time of screening; see [Table 2](#) for the assessments during Part A

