## APPENDIX 17 REVISED SELENA FLARE INDEX

The 2009 revision of the SELENA Flare Index evaluates increases in SLE disease activity within 8 organ systems: mucocutaneous, musculoskeletal, cardiopulmonary, hematological, constitutional, renal, neurological, and gastrointestinal.

Within each organ system, the investigator assesses clinical manifestations and treatment recommendations to arrive at a flare categorization as no flare, mild flare, moderate flare, or severe flare. In this study, investigators will assess only the clinical manifestations; therefore, the treatment component of the rSFI organ systems are not shown here. Also, the renal system will be assessed with the OSS Flare Index, and not with the rSFI.

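### Appendix 16: for a reference UPCR between 1 and 5 mg/mg the moderate and severe rows do not meet, so the UPCR flare grade used for the steroid taper can vanish as proteinuria worsens

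*Combined protocol and SAP*

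**What the plan says.** Appendix 16 grades renal flare on creatinine, UPCR and urinary sediment. It has three moderate UPCR rows, chosen by the starting value. For a starting value above 1 mg/mg the row requires "an increase of ≥ 2-fold with absolute UPCR < 5 mg/mg". The row below it has no ceiling: "If baseline UPCR = 0.5 to 1 mg/mg, an increase in UPCR to ≥ 2 mg/mg". The row for a starting value under 0.5 has none either. The only severe UPCR criterion is "and/or an absolute increase in UPCR > 5 mg/mg".

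Appendix 17 states that "the renal system will be assessed with the OSS Flare Index, and not with the rSFI", so the renal panel printed there cannot supply a missing grade.

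Section 6.6.1 makes the grade operative. A moderate or severe grade on either flare index means the steroid dose is not to be reduced. Without such a grade, randomized subjects on corticosteroids follow the taper. The same section says flare is judged against the previous visit. Appendix 16 instead speaks of *baseline* and does not say which visit that is. Elsewhere the word points to Visit A4: "Results from Visit A4 will be the baseline values for Part B" (Table 2, chemistry and hematology) and "24-hour urine specimens will be used for the UPCR at baseline (Visit A4" (Section 3, note).

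**The concern.** A severity scale should not lose its grade as the measurement gets worse. Here the moderate row ends at a UPCR level of 5, while the severe row begins at a UPCR increase of 5. These two points coincide only if the reference is zero, and the capped row applies only above 1. A subject whose proteinuria passes 5 can therefore drop out of the moderate grade without reaching the severe one. On UPCR alone, the instruction to hold the taper would lapse as the kidney finding worsened.

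A smaller issue sits beside it. Flare is first graded at Visit B2, and the visit before it, B1, has no chemistry scheduled in Table 3 and an empty UPCR cell.

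**Working it through.** No sample size or power figure is involved; the check applies the printed inequalities.

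**Inputs (Appendix 16).** Let *b* be the reference UPCR and *x* the current UPCR, both in mg/mg. The severe UPCR criterion is taken to apply at any *b*, as its and/or wording suggests.

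- Moderate, *b* < 0.5: *x* ≥ 1
- Moderate, *b* from 0.5 to 1: *x* ≥ 2
- Moderate, *b* > 1: *x* ≥ 2*b* and *x* < 5
- Severe: *x* − *b* > 5

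**Step 1: reference 2.** Moderate needs 4 ≤ *x* < 5; severe needs *x* > 7.

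- *x* = 4.9: at least 2-fold and below 5, so moderate.
- *x* = 5.0: not below 5; increase 3.0. No criterion met.
- *x* = 7.0: increase exactly 5.0, not above 5. No criterion met.
- *x* = 7.1: increase 5.1, so severe.

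**Step 2: any reference above 1.** Rises of at least 2-fold that meet no UPCR criterion run from max(2*b*, 5) to *b* + 5. This band exists while 2*b* ≤ *b* + 5, that is, for *b* up to 5. Its width is *b* when *b* ≤ 2.5 and 5 − *b* after that.

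| Reference | Moderate | No UPCR criterion (≥ 2-fold) | Severe |
|---|---|---|---|
| 1.5 | 3.0 to < 5.0 | 5.0 to 6.5 | > 6.5 |
| 2 | 4.0 to < 5.0 | 5.0 to 7.0 | > 7.0 |
| 2.5 | none | 5.0 to 7.5 | > 7.5 |
| 3 | none | 6.0 to 8.0 | > 8.0 |
| 4 | none | 8.0 to 9.0 | > 9.0 |
| 5 | none | 10.0 only | > 10.0 |

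Moderate is unreachable once 2*b* ≥ 5, that is, from *b* = 2.5 upward.

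**Step 3: contrast with the uncapped rows.** From 0.4, moderate runs from 1.0 to 5.4 and severe starts above 5.4. From 1.0, moderate runs from 2.0 to 6.0 and severe starts above 6.0. Neither leaves a gap. There is also a jump at the row boundary: a rise from 1.00 to 5.5 is moderate, but a rise from 1.01 to 5.5 (increase 4.49) meets nothing.

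**Step 4: creatinine rows.** Below 2 mg/dL, moderate is a rise of 0.2 to 1.0 and severe a rise above 1. At 2 or more, moderate is 0.4 to 1.5 and severe is above 1.5. These join, so the fault lies in one UPCR row. The severe creatinine line reads "If baseline creatinine ≥ 2 mg/mg, an increase of > 1.5 mg/mg", where the other creatinine lines use mg/dL; that is clerical.

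**Step 5: reference at Visit B2.** Table 3 starts flare grading, chemistry and first-morning UPCR at B2. Section 8.7.3.2 lists first-morning UPCR for all visits in Parts A and B, which might add one at B1, but it adds no creatinine. Read literally, the previous visit gives B2 no scheduled creatinine reference and an uncertain UPCR one. If Visit A4 is meant, both a spot and a 24-hour UPCR exist there, and the protocol does not say which applies.

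**Step 6: reach into endpoints.** Complete renal response needs UPCR ≤ 0.5 (Section 9.3.3), and every ungraded value is at least 5.0. Moving from one to the other is a fall of (5.0 − 0.5)/5.0 = 90%.

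**The case against.** The strongest reply is that the practical effect is small. Creatinine may still grade a subject in the band. Section 6.6.1 leaves room for investigator judgement, and where there is no flare but some other reason not to taper, it refers the case to Central Review Services and a Therapeutic Expert. Section 4.1.6 also gives that service a role in reviewing flares. All of this stands. A reader might infer that a subject in the band must be tapered; the documents do not say so.

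A second reply is that the gap turns on one word in a table taken from a cited instrument. If the severe row meant a level above 5, then from a reference of 2 only a value of exactly 5.0 would be ungraded. But the text says increase. Whether that is the instrument's wording or a transcription slip cannot be settled here, so the finding is the mismatch as printed.

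A third reply concerns the comparator, and it largely succeeds. It is tempting to say that the protocol sets two competing flare references. Section 6.6.1 is the only text that sets a comparator for flare; the passages placing baseline at Visit A4 concern laboratory results, efficacy and stratification. What remains is a wording mismatch and the unstated reference at B2. B1 normally follows A4 by no more than 10 days (Section 4.1.2), so A4 values are an available candidate, but nothing says they are to be used.

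For the same reason, one should not conclude that the whole stratum at or above 3.0 mg/mg can never receive a moderate UPCR grade. "Randomization will be stratified by baseline (Visit A4) 24-hour UPCR", but under Section 6.6.1 the flare reference moves with each visit, and most Part B visits collect a morning void rather than a 24-hour specimen. The stratum statement would hold only on a Visit A4 reference.

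**Conclusion.** The point holds as an internal inconsistency in Appendix 16. For references above 1 and up to 5 mg/mg, rises of at least 2-fold that land between max(2*b*, 5) and *b* + 5 meet no UPCR criterion. The band is widest at a reference of 2.5 (5.0 to 7.5). From 2.5 upward the moderate UPCR grade cannot be reached at all. This rests only on the printed inequalities and on reading the severe UPCR criterion as applying at any reference.

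The consequence is confined to the taper decision in subjects taking corticosteroids, and it is softened as described. The primary analysis is unaffected, and no visible primary or secondary endpoint is a flare rate. A reader might infer that the responder endpoints requiring a successful taper are compromised; the 90% fall shown above makes the band of little bearing there. How many subjects would fall in the band cannot be estimated from the documents. The B2 reference is a secondary clarification, and the mg/mg unit is a clerical correction. The sponsor should correct the table, because a stated rule for a treatment decision is wrong as written.

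**What to change.** The sponsor should:

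- reconcile the moderate and severe UPCR rows of Appendix 16 so that they use compatible quantities and the grade does not fall as UPCR rises, checking the printed wording against the source instrument;
- align *baseline* in Appendix 16 with the comparator in Section 6.6.1;
- state which creatinine and UPCR values, including the specimen type, are the reference at Visit B2;
- correct the creatinine unit in the severe row at the same time.

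The cut-offs and the reference visit are for the sponsor's clinicians to decide; none is proposed here.

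The cost is one appendix table, one sentence in Section 6.6.1 and a clarification letter to sites, with no new data to collect. If it is made as an amendment, Appendix 2 requires ethics committee approval and, where applicable, health authority approval, so it is best bundled with the next planned revision.
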